8.8 Analysis Software

All analyses will be performed using SAS Software version 9.4 or higher.

9. STUDY SUBJECTS

9.1 Disposition of Subjects and Withdrawals

All randomized subjects will be accounted for in this study. The numbers and percentages of subjects in each analysis set, study withdrawals, age subgroups, and major protocol deviations will be presented. Number of subjects per country and site will be presented by vaccine group and overall for the enrolled set.

Statistical Analysis Plan, Protocol Number V87_30

06 MAY 2022 Final Version 1.0

The time the subjects are under observation for safety will be summarized by vaccine group and overall.

10. DEMOGRAPHICS AND OTHER BASELINE CHARACTERISTICS

In general, all tables related to baseline characteristics should include a Total column across vaccine groups.

10.1 Demographics

Age, height, weight and body mass index will be summarized by reporting the mean, standard deviation, median and range, and will be calculated by vaccine group and overall.

In addition, the frequency of age categories will be reported as 6 to < 36 months and 3 to < 9 years (age cohort). The number and percentages of subjects by sex, country, ethnic origin, race, and previous influenza vaccine (within the past 2 years) will be presented by vaccine group and overall.

Demographic data will be tabulated for the All Enrolled, FAS, PPS and Safety sets.

The distribution across all stratification factors (site*age subgroup) will be presented by vaccine group and overall. This table will be presented based on the IRT data and – if different – also for the actual CRF data.

10.2 Medical History

The numbers and percentages of subjects with medical history will be presented by Medical Dictionary for Regulatory Activities (MedDRA) system organ class (SOC) and PT by vaccine group and overall. Medical history data will be tabulated for the All Enrolled, FAS, PPS and Safety Sets.

Statistical Analysis Plan, Protocol Number V87_30

06 MAY 2022 Final Version 1.0

11. IMMUNOGENICITY ANALYSIS

The immunogenicity analysis will be descriptive in nature and focus on the estimation of the treatment effects of each of the 6 vaccine formulations.

11.1 Blood samples

For each visit, the number and percentages of subjects with and without blood draws will be summarized overall and by vaccine group. Data will be tabulated for all enrolled set.

11.2 Primary Objectives Analysis

The primary endpoints in terms of measures of immunogenicity, as determined by the HI and MN assay against the H5N1 pandemic influenza homologous strain include the following:

- Geometric Mean Titer (GMT) on Day 1, Day 22 (3 weeks after the first vaccination) and Day 43 (3 weeks after the second vaccination).
- Geometric mean ratios calculated as follows: Day 22/day 1 or Day 43/Day 1 as determined by HI and MN assays against the homologous H5N1 pandemic influenza strain.
- Percentage of subjects with seroconversion on Day 22 and Day 43.
- Percentages of subjects with HI or MN titers $\geq 1:40$ at Day1, Day 22 and Day 43.

In addition, reverse cumulative distribution plots will be generated to display the distribution of the antibody responses by visit (Day1, Day 22, Day 43 and Day 202) for each of the vaccine groups. The x-axis represents the immunogenicity values, and the scale of the axis is original scale. The y-axis represents the percentage of subjects having at least that immunogenicity value. Due to the discrete values of antibody response, the plot will show a step-wise function. The figures begin at 100%, and then descends to the lowest point on the curve, which is the percentage of subjects having an immunogenicity value equal to the highest observed value.

No hypothesis testing will be applied.

The primary immunogenicity objective analyses will be performed on the PPS Immunogenicity, and will be also performed based on the FAS Immunogenicity if the percentage of subjects excluded from the PPS immunogenicity is greater than 5%.

Statistical Analysis Plan, Protocol Number V87_30

06 MAY 2022 Final Version 1.0

Geometric Mean Titer

Summary statistics (geometric mean, minimum, median, maximum) of the titers will be presented by assessment (Day 1, Day 22, Day 43 or Day 202) and vaccine group for the overall group and separate by each age subgroup.

The analysis model for the GMT will be done using a general linear model on log-transformed (base 10) Day 22 or Day 43 titers as the outcome variable and as covariates: formulation, log-transformed pre-vaccination titer and age subgroup. From this model, adjusted differences in the least square means (on the log scale) will be produced with 95% confidence limits for each formulation versus the standard formulation F with highest dose. The estimated difference and the confidence limits will be back-transformed to obtain an *adjusted GMT ratio* with 95% confidence limits.

Potential interaction between age stratum and treatment effect will be examined by including an interaction term in the model and present the results of the overall interaction test. The analysis will also be done for each age subgroup separately.

Geometric Mean Ratios (GMRs)

Summary statistics (geometric mean, Coefficient of variation, minimum, median, maximum) of the relative increase in titers will be presented by assessment (Day 22 and Day 43) and vaccine group overall and by age subgroup.

The analysis model for the GMR in titers will be done using the same models as mentioned on log-transformed (base 10) (Day 22 titers/Day 1 titers and Day 43 titers/Day 1 titers) as the outcome variable excluding the pre-vaccination titer as covariate.

Analysis of binary endpoints

The number and proportion of subjects achieving the binary endpoints (seroconversion or titer \geq 1: 40) will be summarized by assessment (Day 22 and Day 43) and vaccine group overall and by age subgroup. These summaries will be reported together with the associated two-sided 95% confidence intervals for the proportion according to Clopper-Pearson.

Statistical Analysis Plan, Protocol Number V87_30

06 MAY 2022 Final Version 1.0

The binary endpoints (i.e. percentage of subjects with seroconversion or with titer $\geq 1:40$) will be compared between each of formulations versus formulation F (highest dose) expressed by the differences of proportions with 95% CI using the Miettinen and Nurminen method without adjustment for the age stratum.

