5.1.4 Randomization

Enrolled subjects will be assigned a unique Subject ID manually entered in EDC. Subject information and stratification information (ie, age) are automatically transferred to the IRT system for randomization in a 1:1:1:1:1:1 ratio into 6 treatment groups and automatically assigned a unique pack ID. The subject ID will be the subject's unique identification number for all eCRFs and associated study documentation that will be used for duration of the study. After randomization, the screening number ceases to be used and remains in the screening and enrolment log only. The list of randomization assignments is produced by the IRT service provider and approved by the sponsor or delegate prior to study start.

Randomization will be stratified by age (cohorts of 6 months through <36 months, and 3 years through <9 years) and by site. The age cohorts will be of equal size. Once an age cohort attains its planned size (ie, half of the planned study sample size) the randomization in this age cohort will be blocked.

If for any reason, after signing the ICF/assent, the subject who is eligible and enrolled fails to be randomized, this is called a randomization failure. The reason for all randomization failures should be recorded in the screening and enrolment log and in the source document as specified in the source data agreement (SDA). The information on

subjects who are randomization failures should be kept distinct from subjects who are screen failures, as described in [section 5.1.2, Screening](#).

If for any reason, after randomization the subject fails to undergo treatment, this is an early termination and the reason should be recorded in source document as specified in the SDA. The information on these early termination subjects should be kept distinct in the source documentation from randomization failures.

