4. RANDOMIZATION AND BLINDING

4.1 Method of Group Assignment and Randomization

Approximately 420 subjects \geq 6 months and $<$ 9 years will be randomized to receive either one of 6 formulations of aH5N1 vaccine in a 1:1:1:1:1:1 allocation ratio, stratifying according to site and age cohort (6 months to $<$ 36 months and 3 years to $<$ 9 years). The number of subjects randomized will be approximately in an equal split between the age subgroups.

The subject will be randomized in the IRT/RTSM system. The subject will receive a unique Subject ID that will be used for all eCRFs and associated study documentation for the duration of the study. The list of randomization assignments is produced by the service provider and approved by the Sponsor according to the applicable Sponsor's Standard Operating Procedure (SOP).

The following 6 formulations will be used:

| Arm | Description |
|-----|----------------------------------|
| A | 1.875 μ g + 50% MF59 0.25 mL |
| B | 3.75 μ g + 50% MF59 0.25 mL |
| C | 7.5 μ g + 50% MF59 0.25 mL |
| D | 1.875 μ g + 100% MF59 0.5 mL |
| E | 3.75 μ g + 100% MF59 0.5 mL |
| F | 7.5 μ g + 100% MF59 0.5 mL |

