8. GENERAL ISSUES FOR STATISTICAL ANALYSES

8.1 Adjustment for Covariates

The main statistical analysis includes descriptive statistics for the overall population <9 years of age. Subgroup analyses will be done by age cohort (6 months to < 36 months, 3 to < 9 years). Summary tables will show unadjusted GMTs for each vaccine group by assessment.

Adjusted GMTs will be calculated based on the log-transformed antibody titers at Day 22 and Day 43 using an Analysis of Covariance (ANCOVA) model which includes the log-transformed pre-vaccination antibody titer, age cohort and vaccine group.

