8.3 Multicenter Studies

The study will be conducted in two countries with a total of around 7 sites. The randomization will be stratified by site and age cohort. The effect of country and site will be explored as subgroup analysis provided that the number of enrolled subjects is sufficient.

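### Randomisation is stratified by site, but the GMT and GMR models against formulation F omit site; if sites differ in titre, the 95% limits are conservative, without bias

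*SAP*

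**What the plan says.** Three places make site a stratification factor. Protocol 5.1.4: "Randomization will be stratified by age (cohorts of 6 months through <36 months, and 3 years through <9 years) and by site". SAP 4.1 describes allocation as "stratifying according to site and age cohort", and SAP 8.3 repeats it: "The randomization will be stratified by site and age cohort". The design overviews (protocol synopsis and 3.1, SAP 3) mention age only, but nothing in them excludes site.

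The analysis models carry one of the two factors:

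- **Adjusted GMTs, SAP 8.1:** the ANCOVA "includes the log-transformed pre-vaccination antibody titer, age cohort and vaccine group".
- **Adjusted GMT ratios against F, SAP 11.2:** a linear model on log10 titre with "as covariates: formulation, log-transformed pre-vaccination titer and age subgroup".
- **GMR, SAP 11.2:** the same model "excluding the pre-vaccination titer as covariate", which leaves formulation and age subgroup.
- **Day 202, SAP 11.3:** analysed in the same way as the primary endpoints.

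On scale, SAP 8.3 says: "The study will be conducted in two countries with a total of around 7 sites". On the use of site, it says: "The effect of country and site will be explored as subgroup analysis provided that the number of enrolled subjects is sufficient". SAP 8.5 lists site and country for descriptive subgroup GMTs, and SAP 10.1 tabulates the stratification factors by vaccine group. No reason is given for leaving site out of the models.

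**The concern.** Stratifying by site makes the formulations nearly balanced within each site, so differences between sites largely cancel from the comparison with F. A model without site does not recognise this. It counts any between-site variation as residual error, and the reported interval is then wider than the real uncertainty of the contrast. The usual practice is to analyse by the factors used to randomise. Here the age stratum is carried into the model and the site stratum is not.

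The other uses of site do not fill the gap. A subgroup table, or a table of baseline distribution, adjusts no comparison with F. If the seven or so sites were of equal size (an assumption), each would have 420/7 = 60 children, or 60/6 = 10 per arm, which is too few to read a contrast from.

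What is at stake is precision. The trial tests no hypothesis and justifies its sample size by interval width, and its results are meant to help health authorities choose a formulation.

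**Working it through.** **Inputs from the documents.** SD of log10 HI titre 0.7; 420 randomised; up to 14% excluded; at least 60 evaluable per arm and 30 per arm and age cohort (protocol 8.5, SAP 5); about 7 sites (SAP 8.3).

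**Assumption.** The share r of residual variance that lies between sites, after age cohort and baseline titre, is not in the documents. The values 0, 5%, 10% and 20% are used.

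**1. The plan's own figures.** Limits on a single GMT are 10^(±1.96 × 0.7/√n). At n = 30 this gives 0.562 to 1.780, and at n = 60 it gives 0.665 to 1.504. The plan states 0.56 to 1.78 and 0.67 to 1.50, so it is reproduced.

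**2. GMT ratio against F without site.** SE = 0.7 × √(2/60) = 0.128. With 360 children and 8 fitted parameters there are 352 degrees of freedom, and 10^(t × SE) = 1.784. Within one age cohort (n = 30 per arm) the factor is 2.274. (The match with 1.78 in step 1 arises because 2/60 = 1/30.)

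**3. With site as a fixed factor.** Seven sites cost 6 degrees of freedom (352 becomes 346), and the residual SD becomes 0.7 × √(1 − r). The half-width on the log scale is t × 0.7 × √(1 − r) × √(2/n). This assumes perfect balance within site, so the gain is a best case.

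| r (assumed) | Factor, n = 60 | Factor, n = 30 | Log-scale narrowing, n = 60 |
|---|---|---|---|
| 0 | 1.78 | 2.27 | 0.0% |
| 5% | 1.76 | 2.23 | 2.5% |
| 10% | 1.73 | 2.18 | 5.1% |
| 20% | 1.68 | 2.09 | 10.6% |

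**4. Simulation.** 3,000 trials per row, permuted blocks of 6 within site and age cohort, 14% excluded at random, and seven sites with 30, 20, 15, 12, 10, 8 and 5% of the children. Block size and site sizes are assumptions. The models contained formulation and age cohort, with or without site; baseline titre was not simulated.

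| r | Mean log10 width, without and with site | Narrowing | Coverage without site | Coverage with site |
|---|---|---|---|---|
| 0 | 0.502, 0.503 | none | 95.3% | 95.3% |
| 5% | 0.5000, 0.4904 | 1.9% | 95.5% | 95.3% |
| 10% | 0.4971, 0.4765 | 4.1% | 95.9% | 95.0% |
| 20% | 0.4920, 0.4497 | 8.6% | 96.3% | 94.8% |

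The Monte Carlo error of each coverage figure is about √(0.95 × 0.05/3000) = 0.4 percentage points, so the 5% row cannot be told from nominal coverage. The narrowing is smaller than in step 3 because a few unequal sites realise, on average, only 1 − Σw² = 1 − 0.186 = 0.81 of the nominal between-site variance. Across the simulations run, coverage without site at r = 20% was 96.3% to 96.9%.

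**5. Upper bound on coverage.** With perfect balance, the unadjusted interval covers 2Φ(1.96/√(1 − r)) − 1 = 95.6%, 96.1% and 97.2%. The simulated values lie at or below these.

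These figures are for GMT ratios. The documents give no SD for the log fold increase, so the GMR effect has the same direction but its size cannot be computed.

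**The case against.** The strongest reply is that nothing in the documents shows that sites differ. Every formulation comes in a prefilled syringe. Temperature-deviated vaccine is a reportable deviation that may lead to exclusion, and the per-protocol set requires results inside the visit windows. Testing is done in sponsor-designated laboratories blinded to arm and visit. The SD of 0.7 comes from healthy elderly adults and is not the residual SD after age and baseline titre, so the share that site would add in this model is unknown. The study has no hypotheses or success criteria. Protocol 8.4.2.3 describes the primary summaries without covariate adjustment, and SAP 8.1 keeps unadjusted GMTs in the tables. A move from 1.78 to 1.76 or 1.73 is unlikely to change a descriptive dose judgement.

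Most of this stands as a limit on size and importance. It does not remove the point. SAP 11.2 still specifies adjusted ratios against F with 95% limits, and in an estimation study the width of those limits is the result. The SAP itself treats site and country as worth exploring, so it does not presume that site has no effect.

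A reader might infer that the planned limits are too wide as a matter of fact. The documents do not support that, because they give no between-site variance, and with none the width is unchanged. Nor do they support a reading that the comparison with F is biased: random allocation within site protects it whether or not site is fitted.

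**Conclusion.** The point holds in conditional form, as a minor improvement. If site explains residual variance beyond age cohort and baseline titre, the planned limits against F are conservative and some of the precision bought by stratifying is lost. At 60 per arm and SD 0.7, the factor of 1.78 would fall to at best about 1.76, 1.73 or 1.68 for assumed shares of 5%, 10% and 20%. Simulated coverage of the unadjusted interval is then about 95.5%, 96% and 96.3% to 97%. The 97.2% from the closed form at a 20% share is an upper bound under perfect balance and should not be quoted as the expected coverage.

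As a scale for the best case, a 10% share is worth 1/0.9 = 1.11 times the sample, or about 40 children on 360. If sites do not differ, fitting site neither helps nor noticeably harms. The size rests on the planning SD and on shares that are assumed; the direction rests only on stratification by site.

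**What to change.** Add site as a fixed factor to the GMT and GMR models in SAP 8.1 and 11.2, which also covers Day 202 through 11.3. Add it to the factorial ANCOVA in SAP 11.4 for consistency. Before unblinding, set a rule for pooling small sites with others in the same country, with an explicit threshold such as at least one evaluable child in every arm. Keep the site and country subgroup tables as description. If the sponsor prefers to leave site out, the SAP should give the reason.

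The cost is one term per model, using data already held for randomisation, and about 6 of roughly 350 degrees of freedom (6 of 173 in the analyses by age cohort). The differences in proportions against F are specified without adjustment even for age; that is a separate choice, which this change does not touch.

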11.4 Exploratory Objectives Analysis

A *post hoc* decision will be made if other measurements will be made. If adequate sera are available and depending on assay availability, antibody responses and their persistence to seasonal and/or homologous and/or heterologous pandemic influenza strains as measured by HI, MN and SRH assays may be described at Days 1, 22, 43, and 202 in the same manner as for primary and secondary immunogenicity endpoints. The results will be included in a separate report. An additional exploratory analysis will be conducted making use of the factorial design of the study and assess the impact of the different factors (dose of MF59 and amount of antigen) on the titers and their GMT. For that we use an analysis of covariance model on log transformed (base ten) Day 22 or Day 43 HI (or MN) titers as the outcome variables and terms for covariates: age cohort, dose of MF59 adjuvant, amount of antigen and Day 1 pre-vaccination HI (or MN) titer. Potential covariate interaction effects will also be examined in this model.

Statistical Analysis Plan, Protocol Number V87_30

06 MAY 2022 Final Version 1.0

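### Age enters the GMT and GMR models only as a two-level cohort, so the cohort-specific models have no age term; this costs a little precision but causes no bias.

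*SAP*

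**What the plan says.** SAP 11.2 models the log10 titer at Day 22 or Day 43 on "formulation, log-transformed pre-vaccination titer and age subgroup". SAP 8.1 describes the same ANCOVA, "which includes the log-transformed pre-vaccination antibody titer, age cohort and vaccine group". The output is an adjusted GMT ratio "for each formulation versus the standard formulation F with highest dose". SAP 11.2 adds: "The analysis will also be done for each age subgroup separately". The GMR analysis uses the same models, "excluding the pre-vaccination titer as covariate". SAP 11.3 carries these methods over to Day 202. The exploratory factorial model in SAP 11.4 again uses the two-level term: "age cohort, dose of MF59 adjuvant, amount of antigen and Day 1 pre-vaccination HI (or MN) titer". No model in either document contains continuous age or finer age bands.

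Randomization is stratified by site and age cohort only (protocol 5.1.4; SAP 4.1 and 8.3). Age and/or date of birth is collected at screening (protocol 5.1.2), and SAP 8.7 gives a formula for age in months at Visit 1. Age is summarized by vaccine group and age cohort (protocol 8.4.1). Unadjusted GMTs are also reported (SAP 8.1).

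**The concern.** The primary immunogenicity objective is reported for the total population and for each age cohort. Within a cohort the two-level age term has one value and disappears. That leaves formulation and baseline titer in the GMT model, and formulation alone in the GMR model.

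Baseline titer can stand in for age only as far as the two are correlated. The SAP background describes humans as immunologically naive to a pandemic strain, previous H5N1 vaccination is an exclusion, and values below the quantification limit are set to half that limit. If most Day 1 titers sit at that floor (an inference, since no baseline distribution is given), baseline titer is almost constant and carries little information about age.

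What is at stake is precision, and how a visible age imbalance would be handled. All five ratios share arm F, so an unusual age mix in F would move all five in the same direction. The age table would show this, but no prespecified model would account for it.

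**Working it through.** **Inputs from the documents**
- SD of log10 HI titer: 0.7, taken from studies in healthy elderly (SAP 5).
- Evaluable children per arm and cohort: 30 (SAP 5). Check: 420 × 0.86 / 12 = 30.1.
- Cohort spans: 30 months (6 to <36 months) and 72 months (3 to <9 years).

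**Assumptions, not in the documents**
- Ages are uniform within a cohort.
- log10 titer is linear in age, with a 2- to 4-fold GMT gradient across the cohort. Zero gradient and a steeper case are shown as well.
- The SD of 0.7 is used for both models; the plan gives no SD for the log ratio to Day 1.

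**The plan's own figure.** 10^(±1.96 × 0.7/√30) = 0.562 to 1.780, against the stated 0.56 to 1.78. It reproduces.

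**Ratio to F without age.** The standard error is 0.7 × √(2/30) = 0.1807. With 180 children in six arms, t on 174 df is 1.974, so the half-width is 0.357 on the log10 scale. The limits are the ratio divided and multiplied by 10^0.357 = 2.27.

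**Chance difference in mean age between two arms of 30.** SD = (span/√12) × √(2/30).
- Younger cohort: 8.66 × 0.258 = 2.2 months, 95% range ±4.4.
- Older cohort: 20.78 × 0.258 = 5.4 months, 95% range ±10.5.

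**Effect on the ratio.** With fold gradient G across the cohort:
- Share of variance explained by age: R² = (log10 G)²/12 / 0.49
- Half-width after adjustment: multiplied by √(1 − R²)
- SD of the shift in the log10 ratio: (log10 G)/√12 × √(2/30)

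| Assumed gradient | R² | Log-scale CI narrower by | CI factor | Shift at 1 SD | Shift at 1.96 SD |
|---|---|---|---|---|---|
| None | 0 | 0 | 2.27 | 1.00 | 1.00 |
| 2-fold | 1.5% | 0.8% | 2.26 | 1.05 | 1.11 |
| 4-fold | 6.2% | 3.1% | 2.22 | 1.11 | 1.22 |
| 5.85-fold | 10% | 5.1% | 2.18 | 1.14 | 1.29 |

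For G = 4: (0.602)²/12 = 0.0302, and 0.0302/0.49 = 6.2%. √(1 − 0.062) = 0.969. The shift SD is 0.602/3.464 × 0.258 = 0.0449, and 10^0.0449 = 1.11.

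Relative to the 0.357 half-width, a one-SD shift is 0.0224/0.357 = 6% (2-fold) to 0.0449/0.357 = 13% (4-fold). In the pooled model, with the same gradient in both cohorts, the shift SD falls by √2, to factors of 10^(0.0224/√2) = 1.04 and 10^(0.0449/√2) = 1.08.

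**Validity check.** One cohort of six arms of 30 was simulated 4,000 times at each R² of 5%, 10%, 20% and 30%, using the formulation-only model (the cohort-specific GMR form). Without age, the mean error in the log10 ratio was within 0.007 of zero and 95% CI coverage was 94.7% to 95.5%. The age imbalance is therefore already inside the 2.27-fold factor.

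**The case against.** The strongest reply is that this is not an error. The planned models contain the age stratification factor and, for GMTs, the baseline titer. Chance imbalance in an unadjusted covariate is what a confidence interval allows for. The gain is small, no hypothesis is tested, and there is no success criterion, so no prespecified decision can change. The protocol's primary method (8.4.2.3) is descriptive GMTs, GMRs and proportions; the adjusted ratio to F is a further SAP summary. All of this stands and limits the point to a minor improvement.

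Three stronger readings are tempting, and the documents do not support them.
- **A reader might infer that the ratios to F are biased.** They are not biased on average over randomization, and coverage is nominal. Exclusions from the per-protocol set are a separate matter that an age covariate does not address.
- **A reader might take the protocol 1.1 seroconversion rates, 91% at 6 to 11 months and 97% at 12 to 35 months, as evidence of an age gradient.** They come from a single dose of a different (H1N1) vaccine and are not titers. The full series to 17 years is 91%, 97%, 95% and 91%, which shows no trend. They do not support a 2- to 4-fold gradient.
- **A reader might infer that adjustment removes the imbalance.** That depends on the functional form. The calculation above is linear in age, while log age is the form suggested as an example.

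**Conclusion.** The point holds as a minor precision matter. Age appears in the GMT and GMR models only as a two-level cohort; the cohort-specific models have no age term, and the cohort-specific GMR model has no covariate at all. Chance age imbalance at about 30 per arm is left unadjusted, although age is collected.

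The planned estimates and intervals remain valid. The size rests on a gradient that the documents do not give: zero gain with no gradient, and intervals about 1% to 3% narrower with a one-SD shift of 1.05 to 1.11 under an assumed 2- to 4-fold gradient. It also rests on uniform ages and on an SD of 0.7 taken from elderly subjects.

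**What to change.** In SAP 8.1 and 11.2, prespecify continuous age at Visit 1 as a covariate in the GMT and GMR models, for example log age in months, and state the functional form. Use it alongside age cohort in the pooled model and as the age term in each cohort-specific model. Day 202 follows through SAP 11.3. Keep the unadjusted GMTs as planned.

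The cost is one degree of freedom per model, out of about 173 (GMT) or 174 (GMR) in a cohort of 180, with no new data and no change to conduct. If unblinding has already occurred, leave the planned models as they are and report the age-adjusted version as a labelled sensitivity analysis.

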11.3 Secondary Objectives Analysis

The secondary endpoints are measures of persistence of antibody responses on Day 202 to study vaccine after primary vaccinations, as determined by the HI and MN assays against the H5N1 pandemic influenza homologous strain:

- Geometric mean titers on Day 1 and Day 202 (6 months after the second vaccination) as determined by HI and MN assays.
- Geometric mean ratios calculated as follows: Day 202/Day 1 as determined by HI and MN assays.
- Percentage of subjects achieving seroconversion on Day 202.
- Percentage of subjects with a titer of $\geq 1:40$ on Day 202.

The analysis of the secondary immunogenicity endpoints will be conducted in the same way as described for the primary immunogenicity endpoints.

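### The between-formulation GMR model drops the Day 1 titre and so gives a second ratio versus F, unbiased but usually a little less precise than the adjusted GMT ratio already planned (minor)

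*SAP*

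**What the plan says.** SAP 11.2 lists both GMTs and GMRs as primary immunogenicity endpoints, the latter as "Geometric mean ratios calculated as follows: Day 22/day 1 or Day 43/Day 1".

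For GMTs, the model is fitted to the log10 Day 22 or Day 43 titre with, "as covariates: formulation, log-transformed pre-vaccination titer and age subgroup". It yields adjusted ratios "with 95% confidence limits for each formulation versus the standard formulation F with highest dose". SAP 8.1 also plans adjusted GMTs from a model "which includes the log-transformed pre-vaccination antibody titer, age cohort and vaccine group".

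For GMRs, the SAP says: "The analysis model for the GMR in titers will be done using the same models as mentioned on log-transformed (base 10"), and names the Day 22/Day 1 and Day 43/Day 1 ratios "as the outcome variable excluding the pre-vaccination titer as covariate". No reason is given. The contrast with F is not restated for GMRs; it follows from the reuse of the GMT model.

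SAP 11.3 says that the secondary (Day 202) analysis "will be conducted in the same way as described for the primary immunogenicity endpoints", so Day 202 inherits both models. SAP 11.2 also states: "No hypothesis testing will be applied". Protocol 8.4.2.3 describes GMRs only as back-transformed log means with confidence intervals and specifies no between-formulation GMR model.

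**The concern.** A model for log10(post/Day 1) without the Day 1 titre is a change-score analysis. It treats the slope of post on baseline as exactly 1. If the true slope is different, each formulation-versus-F contrast keeps part of the chance baseline difference between the arms, and the residual variance is larger than it need be.

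The report would then show two ratios versus F, with different confidence limits, for the same children, assay and day, and nothing in the SAP says which one to read. This matters because the trial has no test or success criterion to settle the question, and its stated purpose is to estimate the response to each formulation. Of the linear models in the SAP, this is the only one that leaves baseline out: SAP 8.1, the GMT model and the factorial model in SAP 11.4 all include it.

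**Working it through.** **Inputs from the documents.** SD of log10 HI titre 0.7, from studies in elderly adults (SAP 5). At least 60 evaluable children per formulation, and 30 per formulation and age cohort (SAP 5). Values below the LLOQ are set to half of it, and the HI LLOQ is 1:10, so undetectable HI titres are coded 5 (SAP 8.7).

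**Assumed, because the documents do not give them.** The share of children detectable at Day 1, the spread of their titres (taken as even over 10, 20, 40 and 80) and the slope b of post on baseline (0 to 1).

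**The plan's own figures.** The GMT interval multipliers are 10^(±1.96 × 0.7/√n). For n = 60 this gives 0.67 to 1.50, and for n = 30 it gives 0.56 to 1.78; both agree with SAP 5. The 80% power for a ratio of 2.5 does not reproduce: 60 per group with SD 0.7 and two-sided 0.05 gives 87.0% (t-test). That mismatch is conservative and separate from this point.

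**Step 1: what the exclusion does.** Let sY and sB be the SDs of the post-vaccination and Day 1 log10 titres within an arm. Per-child residual variances are:

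- change score, baseline excluded: sY² + sB² − 2b·sB²
- baseline included (ANCOVA): sY² − b²·sB²
- difference: (1 − b)²·sB²

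The difference is never negative. It is zero only if Day 1 titres are constant or b = 1. The single degree of freedom spent on the covariate is ignored. The statement is about expected precision; in one data set the order can reverse.

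**Step 2: gap between the two ratios.** On the log10 scale the two contrasts differ by about (b − 1) times the baseline difference between the arms. The SD of this gap is |1 − b|·sB·√(2/n).

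**Step 3: adding the covariate.** Writing Y − B = formulation + γB is the same as Y = formulation + (γ + 1)B. The formulation contrasts and their standard errors are therefore those of the GMT model. A least-squares check agreed to below 1e-15.

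**Step 4: baseline SD.** Above the code of 5, the four detectable values lie 0.301, 0.602, 0.903 and 1.204 higher in log10. Their mean is 0.7526 and their mean square 0.6796. With share p detectable, sB² = 0.6796p − (0.7526p)².

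- p = 5%: 0.03398 − 0.00142 = 0.0326, so sB = 0.18
- p = 20%: 0.1359 − 0.0227 = 0.1133, so sB = 0.34

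**Step 5: results with sY = 0.7.** The width ratio is the square root of the variance ratio. The gap is 10^(1.96 × SD of the gap).

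| Detectable at Day 1 | b | Variance, included | Variance, excluded | CI width ratio | 95% gap, n = 60 | 95% gap, n = 30 |
|---|---|---|---|---|---|---|
| 0% | any | 0.490 | 0.490 | 1.000 | none | none |
| 5% | 0.5 | 0.482 | 0.490 | 1.008 | x/÷1.08 | x/÷1.11 |
| 5% | 0 | 0.490 | 0.523 | 1.033 | x/÷1.16 | x/÷1.23 |
| 20% | 0.5 | 0.462 | 0.490 | 1.030 | x/÷1.15 | x/÷1.22 |
| 20% | 0 | 0.490 | 0.603 | 1.110 | x/÷1.32 | x/÷1.48 |

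At b = 1 there is no difference in any row. For scale, the 95% limits of a single contrast with SD 0.7 and 60 per arm are 10^(±1.96 × 0.7 × √(2/60)), that is x/÷1.78.

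**The case against.** The strongest reply is that the plan already contains the efficient analysis. The baseline-adjusted ratio versus F is pre-specified in the same section, so the trial loses no information, and adding the covariate only prints that ratio a second time. An unadjusted fold-rise comparison is a legitimate companion. No test, success criterion or formal decision depends on it. All of this stands, and it is why the point is minor. It does not explain why a second, usually noisier set of ratios should be reported with no statement of which one to read.

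Three stronger readings are tempting, and the documents support none of them.

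- **That the GMR contrast is biased.** Under randomisation any baseline imbalance is chance. The contrast is unbiased and its interval already reflects the extra variance. Imbalance and lost precision are one effect, not two.
- **That the less efficient comparison is the primary one.** GMT and GMR are both listed as primary, and both models stand under SAP 11.2.
- **That the loss is large.** A 23% wider interval needs a baseline SD of 0.5 with zero correlation: √((0.49 + 0.25)/0.49) = 1.23. A 16% shift from a one-SD imbalance needs an SD of 0.5 with correlation 0.2. Under the spread assumed here, sB peaks at about 0.45, with 60% of children detectable. An SD of 0.5 also fits poorly with the plan's premise: SAP 1 describes people as naive to a pandemic strain, protocol 4.2 excludes earlier H5N1 vaccination, and all undetectable titres share one code.

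**Conclusion.** The point holds, as a minor one. The GMR model fixes the baseline slope at 1 without a stated reason. Its contrasts with F are unbiased, but they are less precise than the adjusted GMT ratios whenever Day 1 titres vary and the slope is not 1, and they can differ from those ratios.

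For the homologous strain the effect is probably small: nothing if no child is detectable at Day 1, and an interval about 1% to 3% wider if 5% are. The gap between the two ratios is the more visible consequence, at x/÷1.08 to 1.16 with 60 per arm and x/÷1.11 to 1.23 with 30 per arm within an age cohort. With 20% detectable the interval is about 3% to 11% wider.

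These sizes rest on the assumed Day 1 distribution, a slope between 0 and 0.5, and an SD of 0.7 that comes from HI titres in elderly adults and is carried over here to children. The documents give no corresponding SD for MN. The direction of the effect does not depend on these assumptions. If seasonal strains are tested under SAP 11.4 by the same methods, Day 1 titres may vary more, since earlier influenza vaccination is allowed and tabulated.

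**What to change.** In SAP 11.2, and for Day 202 through SAP 11.3, do one of two equivalent things:

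- include the log10 Day 1 titre in the GMR model, and state that its formulation contrasts then coincide with the adjusted GMT ratios; or
- name the adjusted GMT ratio as the only between-formulation measure and drop the GMR contrasts.

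In either case keep the unadjusted within-arm GMRs with 95% confidence intervals as the descriptive result, as protocol 8.4.2.3 describes.

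The cost is one model term or one deleted comparison, plus a sentence in the SAP, best made before unblinding. No child is lost, because the GMR outcome already needs the Day 1 titre. The protocol needs no change.
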